9.2 Primary outcome

The primary outcome in this trial is change in the KOOS Pain score from baseline to 3 months.

9.3 Secondary outcomes:

- Baseline to 3 month change in KOOS ADL
- Baseline to 3 month change in EQ-5D
- Treatment failure at 3 months
 - Defined as failing to achieve an 8-point improvement in KOOS pain from baseline and/or receiving injection or undergoing knee surgery prior to 3 months
- Baseline to 3 month change in 40 meter face-paced walk
- Baseline to 3 month change in number of repetitions in sit-to-stand test
- Baseline to 3 month change in single leg balance
- Baseline to 3 month change in muscle strength
 - o Quadriceps
 - o Hamstrings
 - o Gluteus medius
- Durability of pain relief
 - o Treatment Durability: Defined only for those participants achieving ≥ 8 point improvement in KOOS pain from baseline to 3 months, and who did not have an injection or knee surgery during this interval. Treatment durability will be defined as maintaining at least an 8-point improvement at the 12-month follow-up. Participants who receive injection or had knee surgery between 3 and 12-months will be classified as failing to achieve treatment durability.
- Longitudinal Outcomes:
 - KOOS pain at 3, 6, and 12 months
 - KOOS ADL at 3, 6, and 12 months

9.4 Analysis Populations

The primary analysis will be intention-to-treat, where each subject will be analyzed according to the randomization assignment, regardless of treatment received.

A secondary adherers analysis will exclude participants randomized to arms 3 or 4 who do not complete at least 8 in-person PT sessions.

A sensitivity analysis will exclude participants randomized between January and March 2020 to account for the lack of in-person PT during the first months of the COVID-19 pandemic.

A sensitivity analysis will exclude participants with protocol violations that affect eligibility or data integrity, including participants that were randomized but later found to be ineligible, participants receiving the incorrect PT protocol, and participants with incorrect index knee specified on the physician diagnosis form (see section 10.5).

10 Summary of Study Data

Study data will be summarized overall and by treatment group. Continuous data will be summarized by mean (SD) or median (IQR) range, as appropriate. Categorical data will be summarized by frequency and percent.

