8.3 Blinding

This trial is a single-blind study. The Analysis Core, including the Statistician and Principal Investigator, will be blinded to the subject's treatment assignment to avoid bias. Research coordinators communicating with the TeMPO subjects about outcomes assessment and performing follow-up assessments (i.e., performance tests, strength testing) are blinded to the subject's arm assignment. All other individuals, including the study subject, are not blinded. All subjects will be told during the informed consent procedure that this study has a placebo element. However, we will not specify what the placebo element is. Subjects will also be informed that all groups will receive at least some active intervention. The analysis will be done with group status masked; identification of each arm will not be revealed until the analyses are completed.

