8.5 Sample Size

We power the trial to detect a modest effect of 0.33 SD, reasoning that patients and clinicians will adopt treatments with modest effects if the intensity of treatment and risk of harm is low. As the KOOS Pain scale had a baseline SD of 16 points in MeTeOR, an effect size of 0.33 SD equates to 5.3 points, less than the estimated minimally clinically important difference for the KOOS Pain scale of 8-10 points^{9,13}. We envision that the difference between Arm 1 (least intensive) and Arm 4 (most intensive) will be 10-12 points and that the comparisons of Arms 1 vs. 2 (effect of adherence optimization), 2 vs. 3 (additional provider interaction), and 3 vs. 4 (additional therapist-directed exercise and manual therapy) will represent components of this overall difference. Thus, our plan to power for a difference of 5.3 points in pairwise comparisons should provide adequate power for all contrasts. We assume 80% power and Type I error of 0.0167 to reflect three comparisons of strategies that would be used in practice (Arms 4 vs. 1; Arms 4 vs. 2; Arms 2 vs. 1). Given these considerations and balanced allocation across arms, each Arm would need 194 subjects. Allowing for 10% dropout at one year we will require 194 x 1.1 = 214 subjects per Arm, 856 in total.

9 Analytic Considerations

9.1 Hypotheses

This study will address the following hypotheses, summarized in Table 2:

| Table 2. Study Hypotheses | | | | | | | | | | | |
|---------------------------|-----------------------|--|-----------------------|------------------------------------|--|--|--|--|--|--|--|
| Arm | Arm 1 (home exercise) | Arm 2 (home exercise w/adherence optimization) | Arm 3 (placebo PT) | Arm 4 (therapist- delivered PT) | | | | | | | |
| Arm 1 | | | | | | | | | | | |
| Arm 2 | H3 | | | | | | | | | | |
| Arm 3 | | H4 | | | | | | | | | |
| Arm 4 | H1 | H2 | H5 | | | | | | | | |

Primary Hypotheses:

Hypothesis 1: Arm 4 (protocolized home program, adherence optimization, in-clinic physical therapist-delivered exercise and manual therapy) is more efficacious than Arm 1 (protocolized home program alone). This analysis contrasts the putatively most potent intervention against the least potent.

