Hypothesis 2: Arm 4 (protocolized home program, adherence optimization, in-clinic physical therapist-delivered exercise and manual therapy) is more efficacious than Arm 2 (protocolized home program with adherence optimization). This contrast isolates the effect of the in-clinic physical therapist-delivered intervention of exercise and manual therapy.

Hypothesis 3: Arm 2 (protocolized home program with adherence optimization) is more efficacious than Arm 1 (protocolized home program without adherence optimization). This contrast isolates the effect of the adherence optimization program.

Secondary Hypotheses:

Hypothesis 4: Arm 3 (protocolized home program, adherence optimization, in-clinic placebo PT) is more efficacious than Arm 2 (protocolized home program with adherence optimization). This contrast isolates the effect of attending an in-clinic program that provides face to face contact and support by clinicians with essentially no physiological effect directed at musculoskeletal impairments.

Hypothesis 5: Arm 4 (protocolized home program, adherence optimization, in-clinic physical therapist-delivered exercise and manual therapy) is more efficacious than Arm 3 (protocolized home program with adherence optimization and placebo PT). This contrast compares the effects of "active" PT and placebo PT, both given along with protocolized home exercises.

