10.3 Adherence

Adherence will be described in arms 3 and 4 by the mean, median, and range of the number of in-person PT visits attended.

All subjects will be asked to complete a brief home exercise adherence log once every two weeks from randomization through 3 months We will also describe self-reported adherence to exercise for all arms.

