11.1 Primary Analysis

In the primary analysis we will test the 3 hypotheses outlined in section 7.1. As placebo is not used in practice, we do not consider tests involving Arm 3 as one of our multiple comparisons. For the primary analysis the alpha level is adjusted to 0.0167 to account for 3 comparisons. We will adjust for randomization arm, the randomization stratification factors of study site and baseline KL grade (0-2 vs. 3) as well as baseline KOOS pain and enrollment date (prior to or after March 15, 2020).

We will use linear regression as our main analytic approach, as our primary outcome of change in KOOS pain is continuous. The primary analysis will be complete case. Data will be summarized by treatment group with the number, mean, and standard deviation. 98.3% Cis will be used to summarize the three between-group comparisons of interest.

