11.5 Statistical analyses to handle missing data

We anticipate ~5% dropout at 3 months and ~10% at 12 months based on dropout rates from the Meniscal Tear in Osteoarthritis Research (MeTeOR) RCT⁹. We will address dropout and other forms of missing data first by reporting the number of subjects dropping out in each arm and the reasons for dropout. We will determine whether the frequency of these dropouts differs across study arms. We will examine the distribution of baseline covariates and baseline KOOS pain in subjects dropping out compared to those completing the study. Our primary assumptions

are that data will be missing at random (MAR), and that dropout will not depend on unobserved outcomes.

We will perform sensitivity analysis for missing data for our primary outcome of KOOS pain and our secondary outcomes of KOOS ADL, EQ-5D, strength measures, objective function measures, and treatment failure for our three primary hypotheses. We will use linear mixed effects models to analyze the continuous outcomes of KOOS pain, KOOS ADL, and EQ-5D. Models will be adjusted for timepoint, randomization arm, the randomization stratification factors of study site and baseline KL grade (0-2 vs. 3) as well as the baseline value of the outcome and enrollment date (prior to or after March 15, 2020). A timepoint by treatment arm interaction term will test whether change from baseline to 3 months differs between treatment arms. Linear mixed-effects models can handle imbalanced data and are appropriate for data that are missing at random.

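### The adherers analysis removes low attenders from Arms 3 and 4 only, so any contrast it makes with Arm 1 or 2 is not randomized and should be labelled so

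*SAP*

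**What the plan says.** SAP 9.4 makes intention-to-treat the primary analysis and then adds: "A secondary adherers analysis will exclude participants randomized to arms 3 or 4 who do not complete at least 8 in-person PT sessions". Table 1 in 8.1 gives 14 in-person sessions to Arm 3 and 14 to Arm 4, and none to Arms 1 and 2. Section 9.4 does not say which hypotheses are examined in this set or how the result should be read.

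Attendance will already be recorded. Section 10.3 says: "Adherence will be described in arms 3 and 4 by the mean, median, and range of the number of in-person PT visits attended".

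Section 9.1 describes H2 (Arm 4 vs 2) as follows: "This contrast isolates the effect of the in-clinic physical therapist-delivered intervention of exercise and manual therapy". For H4 (Arm 3 vs 2) it says: "This contrast isolates the effect of attending an in-clinic program that provides face to face contact and support by clinicians". Section 11.1 sets the level for the primary contrasts: "For the primary analysis the alpha level is adjusted to 0.0167 to account for 3 comparisons". Section 11.6 leaves secondary hypotheses and outcomes without multiplicity adjustment.

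**The concern.** The filter depends on behaviour after randomization and can act on two of the four arms only. Participants in Arms 1 and 2 who would have attended poorly had they been offered sessions all stay in. A contrast of a filtered arm with an unfiltered one therefore mixes the effect of treatment with the difference between people who attend and people who do not. The covariates in 11.1 (site, KL grade, baseline KOOS Pain, enrollment period) may reduce that difference, but they do not capture motivation or early response.

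What is at stake is interpretation. If the adherers estimate differs from the intention-to-treat estimate, a reader may take the gap to be the effect of attending. Part or all of it could be selection.

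**Working it through.** **The plan's own figures.** Section 8.5 uses 0.33 SD with SD 16: 0.33 x 16 = 5.28, given as 5.3 points. With two-sided alpha 0.0167 and 80% power, n = 2 x (2.394 + 0.842)² / 0.33² = 192.3, so 193 per arm; the t-test version gives 193.6, so 194, as the SAP states. These figures only set the scale here. The argument does not rest on them.

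**Which contrasts are one-sided.**

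| Contrast | First arm | Second arm |
|---|---|---|
| H1: 4 vs 1 | filtered | whole arm |
| H2: 4 vs 2 | filtered | whole arm |
| H3: 2 vs 1 | whole arm | whole arm |
| H4: 3 vs 2 | filtered | whole arm |
| H5: 4 vs 3 | filtered | filtered |

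H5 applies the same rule to both arms, but it still conditions on attendance after randomization, which may differ between true and placebo PT.

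**Bias with no true effect.** Let q be the share excluded and g the attender minus low-attender gap in expected improvement. The whole-arm mean is (1 - q) x attender mean + q x low-attender mean. Attender mean minus whole-arm mean is therefore q x g.

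Inputs:
- SD 16 and 214 per arm, from 8.5.
- 3-month dropout, from 11.5: "We anticipate ~5% dropout at 3 months and ~10% at 12 months". This gives 214 x 0.95 = 203 per arm.
- q = 10-30% and g = 0.2-0.4 SD (3.2-6.4 points): assumed, because the SAP gives neither.

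SE = 16 x sqrt(1/203 + 1/(203(1 - q))). Rejection is two-sided at an assumed 0.05.

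| q | g | Bias q x g | Share of 5.3 | SE | Rejection, no true effect |
|---|---|---|---|---|---|
| 0.1 | 3.2 | 0.32 | 6% | 1.63 | 0.054 |
| 0.2 | 4.8 | 0.96 | 18% | 1.68 | 0.088 |
| 0.3 | 6.4 | 1.92 | 36% | 1.75 | 0.195 |

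A negative g reverses the sign with the same rejection rate; g = 0 gives no bias. A different assumed model (a latent attendance trait correlated 0.1-0.3 with improvement, 10-30% excluded) gives 0.3-2.4 points, so the order of magnitude is similar. SD 16 is a baseline SD, and baseline adjustment may shrink both the gap and the residual SD.

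**The complier estimate for 4 vs 2 or 3 vs 2.** Without covariates, two-stage least squares gives the intention-to-treat difference divided by (1 - q).
- Precision: the intention-to-treat SE is 16 x sqrt(2/203) = 1.59, a 95% half-width of 3.1. Dividing by 0.9 to 0.7 gives half-widths of 3.5-4.5, which is 11-43% wider.
- Partial attendance: if low attenders get half of a 5.3-point effect, it returns (5.3(1 - q) + 2.65q)/(1 - q) = 5.6-6.4.
- Unblinded participants (8.3: "All other individuals, including the study subject, are not blinded"): if assignment alone shifts reported pain by an assumed 2 points, it returns 2/(1 - q) = 2.2-2.9 with no session effect.
- Dropout tied to attendance: assume Arm 4 loses 5% overall, with low attenders losing 23%, 20% and 16.7% in the three cases. The observed low-attender share becomes 0.081, 0.168 and 0.263. The error, (q - observed share) x g / (1 - observed share), is 0.07, 0.18 and 0.32 points, against 0.32, 0.96 and 1.92 for the subset.
- Arm 4 vs 1: adherence optimization also differs. With a PT effect of zero and an assumed optimization effect of 5.3, the method credits the sessions with 5.3/(1 - q) = 5.9-7.6.

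**The case against.** The other side has several fair points.

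- The analysis is labelled secondary, the primary analysis is intention-to-treat, and the SAP nowhere claims that the adherers set preserves randomization. This stands and limits the weight of the point.
- The one-sidedness follows from the design, because only Arms 3 and 4 have sessions. That is true, and it explains the filter, but it does not make the comparison randomized.
- A reader might infer that H1, H2 and H4 are certain to be run in this set. Section 9.4 names no contrasts, and the appendix tables listed in section 14 include none for adherers, so the documents do not establish this. The point is conditional on that use.
- A reader might also infer that the wording about isolating effects in 9.1 contradicts 9.4. It does not: it describes the hypotheses and makes no claim about the adherers set.
- A reader might call the absence of an alpha level for this analysis a defect. Section 11.6 leaves secondary hypotheses and outcomes unadjusted. It does not mention the adherers set by name, so at most a clarification is due.
- The complier estimate has biases of its own. With partial benefit it overstates a 5.3-point effect by 0.3-1.1 points even when attendance is unrelated to prognosis, a case in which the simple subset is unbiased for attenders. This stands. It is a reason to report the two side by side and not to present the complier estimate as the unbiased replacement.

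**Conclusion.** The point holds as a minor issue of interpretation. Used for Arm 3 or 4 against Arm 1 or 2, the adherers analysis compares selected attenders with everyone randomized to the other arm, and nothing elsewhere in the SAP corrects or flags this. The sign of the bias is unknown. Its size is about 0.3-1.9 points under the assumed 10-30% exclusion and 0.2-0.4 SD gap before baseline adjustment, and zero if attendance is unrelated to prognosis. The upper end pairs both extreme assumptions.

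The documents do not support the stronger inference that the trial's main result is at risk: the primary hypotheses are tested by intention-to-treat, which this rule does not touch.

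**What to change.** In 9.4:

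- Name the contrasts the adherers analysis covers. Keep the subset result, but label it a non-randomized, exploratory comparison for every contrast with a filtered arm, including Arm 4 vs 3. If wanted, one clause can confirm that the no-adjustment rule in 11.6 applies.
- For Arm 4 vs 2 and Arm 3 vs 2, add a complier-average causal effect by two-stage least squares, with randomized arm as the instrument for completing at least 8 sessions and the primary-model covariates. Add a check with number of sessions attended as the exposure.
- Do not use this for Arm 4 vs 1; report intention-to-treat there.
- State the limits: the estimate is a rescaled intention-to-treat result and not a new test. It is overstated if partial attendance has benefit or if knowing the assignment shifts reported pain, and it needs outcomes missing at random.

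The cost is a few sentences and a few extra models on attendance data already collected. The price in precision is the wider interval shown above. If the extra models are not wanted, naming the contrasts and labelling the results would by themselves guard against the misreading.

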10.1 Participant Disposition

Participant disposition will be summarized in a CONSORT diagram.¹⁴ This will include the number of patients screened for eligibility, the number of patients eligible, the number of patients interested, the number of patients randomized, and the number of patients randomized to each treatment group. The reasons for ineligibility will also be summarized as part of the CONSORT diagram.

Visit completion status and the reason for early discontinuation of the study will be summarized by site and treatment arm with descriptive statistics. These include the number and percentage of each reason for discontinuation. We will also summarize the number and percent of participants undergoing APM by timepoint and undergoing injection by timepoint.

10.2 Demographic and Baseline Variables

Baseline characteristics will be summarized overall and by treatment group and presented in a table. These include:

- Site
- Sex
- Race
- Ethnicity
- Educational attainment
- K-L Grade
- Age
- Body Mass Index
- Enrollment date (prior to or after March 15, 2020)

We will also present the baseline value of the primary and secondary outcomes.

10.3 Adherence

Adherence will be described in arms 3 and 4 by the mean, median, and range of the number of in-person PT visits attended.

All subjects will be asked to complete a brief home exercise adherence log once every two weeks from randomization through 3 months We will also describe self-reported adherence to exercise for all arms.

10.4 Data collected outside of visit window

The windows for data collection are shown in the table below:

| Form | Timeframe (based off intervention start unless noted) |
|---------------------------------------|---|
| Baseline Questionnaire and Assessment | Any time before randomization |
| 3-Month Questionnaire and Assessment | 12-16 weeks after randomization |
| 6-Month Questionnaire | 22-26 weeks after randomization |
| 12-Month Questionnaire | 46-50 weeks after randomization |

We anticipate that some study assessments may be completed outside of the visit window (for example, a subject may have to postpone a scheduled visit for a week or two because of a death in the family). We will summarize the number and percentage of assessments completed outside of the ideal window separately for questionnaire completion and performance assessments. If necessary, sensitivity analyses will be undertaken to examine if the conclusions about the study outcomes are affected by the exclusion of out-of-window visits.

10.5 Protocol violations

Violations will be summarized overall and for each arm of the study. The number of participants with violations and the frequencies and percentages of the types of protocol violations will be presented. The pre-specified list of protocol violations is presented below:

Protocol violation: Noncompliance with or divergence from IRB-approved protocol that does negatively affect 1) the patient's safety, welfare or eligibility, or 2) the integrity of the data. In particular, this includes any instance in which exclusion criteria, randomization criteria, discontinuation criteria, or confidentiality procedures are applied in a way that diverges from study protocol. Examples include:

- · Incorrectly enrolling an ineligible patient
- Missing MRI or x-ray
- Sending a subject materials for an arm to which the subject was not randomized
- Breaches of HIPAA
- Inadequate/missing informed consent
- Unreported SAEs
- Unblinding a party that should be blinded
- Performing the incorrect PT protocol with a subject (e.g. an arm 4 subject receives ultrasound)
- First PT visit (arms 3 and 4) occurring more than 30 days after the scheduled intervention start or not at all.

11 Analytic Approach

11.1 Primary Analysis

In the primary analysis we will test the 3 hypotheses outlined in section 7.1. As placebo is not used in practice, we do not consider tests involving Arm 3 as one of our multiple comparisons. For the primary analysis the alpha level is adjusted to 0.0167 to account for 3 comparisons. We will adjust for randomization arm, the randomization stratification factors of study site and baseline KL grade (0-2 vs. 3) as well as baseline KOOS pain and enrollment date (prior to or after March 15, 2020).

We will use linear regression as our main analytic approach, as our primary outcome of change in KOOS pain is continuous. The primary analysis will be complete case. Data will be summarized by treatment group with the number, mean, and standard deviation. 98.3% Cis will be used to summarize the three between-group comparisons of interest.

11.2 Secondary Analyses

11.2.1 Secondary Hypotheses

In a similar fashion to the primary analysis, we will test the two secondary hypotheses outlined in section 7.2 for the outcome of 3 month KOOS pain.

11.2.2 Secondary Outcomes

All models will adjust for randomization arm, the randomization stratification factors of study side and baseline KL grade (0-2 vs. 3) as well as baseline value of the outcome and enrollment date (prior to or after March 15, 2020). We will adopt an intention-to-treat approach.

We analyze 3 month KOOS pain with an Analysis of Covariance adjusted for baseline KOOS pain. (This approach uses the 3 month value, adjusted for baseline, as the outcome, rather than the difference between three months and baseline).

11.2.2.1 Continuous secondary outcomes for baseline to 3 month change (KOOS ADL, EQ-5D, performance measures)

We will analyze continuous secondary outcomes with linear regression additionally adjusting for the baseline value of the outcome. In the case that some measures deviate from a normal distribution (e.g., number of repetitions in sit-to-stand test) we will consider data transformation or a generalized linear model (e.g., Poisson regression).

